2 SUMMARY

PROTOCOL IDENTITY AND AIM

| | |
|-----------------|--|
| NCT-number | NCT xxxxx |
| Protocol title: | Albumin mass balance in liver transplantation. |
| Study aim: | Assess the losses of albumin from circulation during and after liver transplantation and identify predictors of albumin loss |

METHODOLOGY

| | |
|----------------------------|--|
| Study design: | Open explorative physiological study |
| Primary research question: | Is cumulative perioperative albumin shift from plasma positive at postoperative day 7? |
| Effect parameter: | Albumin mass balance |
| Safety parameters: | Vital parameters |

INVESTIGATED POPULATION

| | |
|-----------------|---|
| Study subjects: | Patients undergoing liver transplantation |
| Number: | 240 |

TIME PLAN

| | |
|-------------------------|---------|
| First patient included: | Q1 2018 |
| Last patient included: | Q1 2021 |
| Last patient finalized: | Q2 2021 |

3 ABBREVIATIONS

| Abbreviation | Unit | Explanation |
|---------------------|-------------|---------------------------------------|
| ASR | mg/kg/day | Absolute Synthesis Rate |
| Bq | | Becquerel, radiation dose |
| CPAS | g | Cumulative perioperative albumin loss |
| CRF | | Case report form |
| D ₅ -Phe | | Deuterium labeled phenylalanine |
| FSR | %/day | Fractional Synthesis Rate |
| MELD | | Model for End-Stage Liver Disease |
| MPE | | Mol percent excess |
| POD | | Post operative day |

5 BACKGROUND

5.1 ALBUMIN IN VOLUME RESUSCITATION

Albumin is a major constituent of plasma proteins, contributing to the colloid osmotic pressure in the capillaries [Kaysen 1998, Margaron 2002]. The association between massive volume overload and poor outcome in surgery and critical illness has contributed to the popularity of colloid solutions for volume resuscitation for the last 50 years. It might seem logic to use exogenous albumin in situations of circulatory instability, in particular when plasma albumin concentration is low. The background is that volume resuscitation employing a colloid like

albumin may be achieved with less than half the fluid volume as compared to isotonic crystalloid solutions, which has been demonstrated repeatedly in healthy subjects [Groeneveld 2011]. In situations characterized by low blood pressure, the immediate effect upon blood pressure of a colloid like albumin is also very convincing in a short time perspective [Margaron 2002]. However, in blinded randomized studies of patients with severe sepsis or septic shock, the volume needed to resuscitate is not dramatically different between groups given a colloid based regimen as compared to a crystalloid based regimen [Annane 2013, Finfer 2004, Myburgh 2012, Perner 2012]. In addition, there is no consistent outcome advantage for the patients randomized to be given a colloid containing protocol [Delaney 2011, Dellinger 2013, Perel 2013].

The explanation sought for this discrepancy between the situation in healthy subjects and patients with an assumed increase in capillary leakage on one hand, and the short term obvious effect seen on for example blood pressure after colloid administration, has been efforts to select the patients that are most compromised in terms of circulatory shock [Caironi 2014].

Today, after the recommendation against the use of hydroxyethyl starches as a synthetic colloid of the European Medical Agency for safety reasons, albumin containing solutions remain the only alternative when the use of a colloid is preferred. This is also reflected in existing international guidelines that recommend considering the use of albumin containing solutions when resuscitation with crystalloid solutions only seems insufficient [Rhodes 2017]. This is despite the absence of solid evidence for this treatment strategy in long term outcomes.

5.2 ALBUMIN IN LIVER TRANSPLANTATION

End-stage liver failure is associated with high mortality, unless treated by liver transplantation. Almost 100 liver transplantations are performed yearly at Karolinska University Hospital Huddinge. Of these, 5-10 recipients are children, and 10-20% of the patients will stay in the ICU for more than 3 days after the liver transplantation. Some of these patients have large losses in drains and in children these losses can amount to 10-30% of total body weight per day. There is very sparse literature or evidence for guidance in the treatment of these patients. At our unit, fluid losses are largely treated by infusions containing albumin, but there is little scientific support for this routine. A more systematic assessment of these patients would be of great value for future guidelines.

In a recent pilot study on selected patients undergoing liver transplantation (EPN D-nr 2015-1048-31/2), we found a cumulated loss of albumin until the 3rd post-operative day (POD3) of 48 ± 33 g. There was a wide variation but in contrast to patients undergoing major abdominal surgery [Norberg 2016] the loss seemed to persist from end of surgery to end of study. Furthermore, albumin synthesis rate was recovered at POD3 in this cohort of patients. This pilot study demonstrated the feasibility of a concept using albumin mass balance and measurement of synthesis rate of liver export proteins (albumin and fibrinogen) to characterize albumin losses from the plasma compartment and albumin physiology. The pilot study excluded patients with major peroperative bleeding, re-operations and other risk factors for a complicated post-operative course. Therefore, in order to extend both the internal and external validity of our observational study, we plan to recruit consecutive patients undergoing liver transplantation and to prolong the albumin mass balance part of the study primarily until POD7, but if applicable to POD21 or hospital discharge.

Isotopic analysis of albumin synthesis rate will be performed in the above mentioned patients that are in the ICU at POD4 and might be repeated after 3-10 days. Although albumin synthesis increases in connection with inflammation, liver transplantation represents a special case in several ways. Some degree of ischemia and liver cell injury is always present after

surgery, possibly affecting synthesis capacity for some time. Bleeding and fluid shifts are sometimes great, and losses in drains after surgery might be profound. The use of immunosuppressive drugs bound to albumin makes interpretation of drug concentrations difficult if plasma albumin varies too much over time. In our hospital a plasma albumin of 25 g/L is routinely used as target post-operatively.

5.3 ALBUMIN MASS BALANCE CALCULATIONS

By rigorous measurement of losses and gains of albumin during and after surgery, i.e. assessing bleeding, losses in drains, urine etc and measuring hemoglobin and albumin in plasma samples and in all blood products given, it is possible to calculate the loss of albumin from plasma that is not accounted for by other means. This is the cumulative perioperative albumin shift (CPAS) that represents albumin lost from the blood by capillary leakage or catabolism.

In major gynecological cancer surgery protein loss was reported as 49 g [Rehm 1998], and after major abdominal surgery cumulative perioperative albumin shift was 19 g (range 2-61) [Norberg 2015]. In liver transplantation the perioperative albumin loss was 37 ± 17 g (EPN D-nr 2015-1048-31/2, preliminary results) at end of surgery.

Blood sampling outside clinical routine for albumin mass balance calculations will not exceed 40 ml during a 21 day period. For children there is no study specific blood sampling at all for the mass balance analysis.

5.4 ALBUMIN DE NOVO SYNTHESIS

Albumin is synthesized in the liver at a rate of 150 mg/kg/day, or 13 g/24 h [Barle 2002]. This corresponds to a fractional synthesis rate of 6-8 %/24 h in a healthy subject with a plasma volume of 3 liters and 120 g of albumin in the intravascular space [Kaysen 1998]. In addition there is another 180 g of albumin in the interstitial space. These two compartments are in equilibrium by capillary leakage of 5 % per hour that is returned to the vascular space through the lymph flow. In states of an increased capillary leakage or circulatory instability, these figures may be dramatically altered [Margaron 2002].

Albumin synthesis rate is determined by incorporation of isotopically labeled amino acids into albumin [Ballmer 1990]. Today the most common technique is to use deuterated phenylalanine given as a flooding dose. De novo synthesis of albumin is stimulated by food intake, while it is decreased in states of liver insufficiency [Caso 2007, Ballmer 1996].

The blood sampling volume for one measurement of albumin synthesis will be 20 ml.

5.5 MARKERS OF ENDOTHELIAL INJURY AND INFLAMMATION

The mechanism of albumin loss is not well uncovered but increased capillary leakage in connection with fluid overload and inflammation are likely to contribute. Several substances have been suggested as markers of endothelial injury. Commercial enzyme-linked immunoabsorbant assay (ELISA) kits are available for syndecan-1, hyaluron, heparansulphate etc. They represent components of the glycocalyx that are suggested to be flaking in inflammation or injury. Heparin binding protein has been suggested as a mediator of capillary leakage and is also measured by ELISA. Interleukins 6, 8 and 10 are early markers of inflammation and are likewise measured by ELISA. CRP is a too slow parameter to be of relevance in this context, but will be routinely measured and presented.

The field is rapidly developing and possible new ELISAs in the field of glycocalyx function, injury or inflammation might be considered for this investigation.

The blood sampling volume for one measurement by ELISA will be 4 mL for adults and 2 ml for children. This is the only blood sampling in children.

6 STUDY AIMS

6.1 MAIN STUDY

The primary aim of the main study is to measure if the cumulative perioperative albumin shift is normalized on POD 7 in patients undergoing liver transplantation at Karolinska Huddinge.

Secondary aims are to compare the loss at POD 7 with that at EOS and POD 3, the albumin loss at hospital discharge, and to explore predictors of increased albumin shift from plasma.

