7 RESEARCH QUESTION

7.1 PRIMARY QUESTION

Is cumulative perioperative loss of albumin from plasma positive at post-operative day 7 (4-10) after liver transplantation?

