8 ENDPOINTS

8.1 PRIMARY ENDPOINT

Cumulative perioperative albumin shift (CPAS) by mass balance at POD 7 (4-10).

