17.3 DETERMINATION OF THE NUMBER OF SUBJECTS

On page 4 we state that the number of subjects is 240 in the main study. This refers to an overestimation of the total number of liver transplantations during a approximately 2 year period at our hospital and the primary outcome of albumin mass balance.

The primary endpoint of the study (cumulative perioperative albumin shift at POD7) has never been investigated before. On POD3 48 ± 33 g, $p=0.0017$ versus baseline was found in our previous study on selected patients undergoing liver transplantation [Amouzandeh 2017]. This corresponds to a effect size of 1.4. Although data in consecutive patients are likely to be even more scattered a power of 90% is reached with $n=100$ for an effect size of 0.33 with a one sample 2-sided t-test and a significance level of 5%.

We plan to do linear regression with the thus detected “leakiness” as dependent variable and look at possible predictors. We will also dichotomize the patients in “leaky” and “not so leaky” (cut off to be estimated by ROC-curve analysis) and explore possible predictors by logistic regression and multiple logistic regression. The size of the data base becomes important to the quality of the multiple regression procedure, but data quantity will be governed by our patient flow and research resources. Data collection over much more than 2 years is likely to be confounded by changes in routines over time.

The large number of correlations mentioned above must be seen against the background that this is an exploratory pilot study of albumin mass balance and albumin kinetic parameters in liver transplantation. Because this is an unselected patient group for this kind of measurements, there is an intention that the study also should be hypothesis generating.

Sub study A (children, n=20) is included in the above mentioned number.

Sub study B (prolonged ICU stay, n=20) is a cohort included in the main study above.

The expected numbers in substudies A and B are the main reason to extend the whole study to approximately 2 years, and are based on historical records. Although data are likely to be scattered, with n=10-20 there is a reasonable chance to perform statistical inference analysis. The groups will also be compared with the complete data set.

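### Section 6.1 asks whether CPAS has normalised by POD 7, but the planned test can only show that it is positive; the secondary comparison with EOS and POD 3 is planned as a correlation, which does not measure change

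*Combined protocol and SAP*

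**What the plan says.** The primary aim in section 6.1 reads: "The primary aim of the main study is to measure if the cumulative perioperative albumin shift is normalized on POD 7". The document does not define normalised and gives no reference value or margin for it.

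The summary puts the primary research question differently: "Is cumulative perioperative albumin shift from plasma positive at postoperative day 7". Section 7.1 agrees with the summary: "Is cumulative perioperative loss of albumin from plasma positive at post-operative day 7 (4-10) after liver transplantation". The primary endpoint in 8.1 is CPAS by mass balance at POD 7, with a window of days 4 to 10.

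The only test named for this endpoint is in the sample-size section, 17.3: "a power of 90% is reached with $n=100$ for an effect size of 0.33", using a "one sample 2-sided t-test and a significance level of 5" per cent. Section 17.2, the statistical analysis section, names no primary test. It says that data will be presented as mean with SD, or as median and range.

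The sentence after the primary aim in 6.1 makes it a secondary aim to compare the POD 7 loss with the losses at EOS and POD 3. Question 1 in 7.2 then asks whether these losses correlate. Sections 17.2 and 17.3 plan correlations and regressions, and no estimate of within-patient change.

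**The concern.** There are two gaps between aim and analysis.

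First, showing that CPAS is positive and showing that it has normalised are different tasks. A test against zero can do the first. It cannot do the second, because failing to reject zero is also what a real residual shift produces when the scatter is large. If the answer to 6.1 is taken from this test, a null result has no valid reading in the terms of the aim.

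Second, CPAS is a cumulative quantity, so its level at POD 7 does not say whether the shift rose, stopped or fell after POD 3. The secondary aim is the natural place to answer that. Section 5.2 shows why it matters: the pilot loss seemed to persist to the end of study, and follow-up is being extended to POD 7. A correlation only shows whether patients keep their ranking or relative position. The time course could be left unestimated although the data for it are collected.

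**Working it through.** **Inputs.** From 17.2 and 17.3: pilot CPAS 37 ± 17 g at EOS and 48 ± 33 g at POD 3; two-sided alpha 5%; n=100; effect size 0.33; planned number 240, described as an overestimate of about two years of transplants. Section 5.2 gives almost 100 transplants a year. Section 17.3 says that the POD 7 endpoint has not been studied before and expects more scatter than in the pilot. The POD 7 SDs used here (33, 50 and 66 g) and the POD 7 means are therefore assumptions; 33 g is the pilot POD 3 value and 66 g is twice that. The null value of zero is inferred from the word positive and from the pilot comparison with baseline.

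**The plan's own figure.** For a one-sample two-sided t-test, power comes from the noncentral t distribution with n − 1 degrees of freedom and noncentrality d√n. With d = 0.33 and n = 100 the noncentrality is 3.3 and power is 90.5%. The smallest n for 90% is 99. The stated figure reproduces.

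**What a null result would mean.** Take a true mean of 12 g, a quarter of the pilot's 48 g, with d = 12/SD:

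| Assumed SD | d | Power, n=100 | n=150 | n=200 | n=240 |
|---|---|---|---|---|---|
| 33 g | 0.364 | 95% | 99% | >99% | >99% |
| 50 g | 0.240 | 66% | 83% | 92% | 96% |
| 66 g | 0.182 | 44% | 60% | 73% | 80% |

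For a true mean of 5 g at n=100, the test is non-significant in 68%, 83% and 88% of studies at SD 33, 50 and 66 g. Non-significance is thus compatible with a real residual shift, to a degree that depends on SD and n.

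**What an interval would give.** The 95% CI half-width is t(0.975, n−1) × SD/√n. At n=100 this is 1.984 × SD/10 = 6.5, 9.9 and 13.1 g at SD 33, 50 and 66 g. At n=240 it is 1.970 × SD/15.49 = 4.2, 6.4 and 8.4 g. The interval shows directly which residual shifts remain compatible with the data.

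**What a positive result leaves open.** At n=100, if the mean stayed at the POD 3 value of 48 g, power against zero exceeds 99.9% at SD 33 or 66 g. If it had fallen by half, to 24 g, power is above 99.9% at SD 33 g and 95% at SD 66 g. Both give the answer positive.

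**Why correlation does not fill the gap.** If each patient's POD 7 value is c times the POD 3 value, with c > 0, then r = 1 for any c. With a POD 3 mean of 48 g, c = 0.5 gives a mean change of −24 g and c = 2 gives +48 g. The correlation is 1 in both cases.

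**Precision of the paired change.** With SD 33 g at both POD 3 and POD 7 (an assumption) and correlation ρ, the SD of the change is 33√(2 − 2ρ). For ρ = 0.3, 0.5, 0.8 and 0.9 this is 39.0, 33.0, 20.9 and 14.8 g. At n=100 the 95% CI half-widths are 7.7, 6.5, 4.1 and 2.9 g.

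**The case against.** The strongest reply is that one loose word is being weighed against a consistent plan. Normalised appears once, in 6.1. The summary, 7.1, the children's sub-study aim and questions 2 and 4 in 7.2 all ask whether the loss is positive. The t-test fits that question, and its sample-size arithmetic is right. This stands, and it is why the remedy is to bring 6.1 into line with 7.1 rather than to redesign the test.

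A reader might infer that the investigators will report a non-significant result as normalisation. The documents do not say so, and 17.2 promises means with SDs, so the amount of albumin would be visible. The wording of the aim invites that reading and nothing in the plan rules it out, but that is all that can be said.

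A reader might also infer that a significant result would mislead. It would not: if normalised means zero, a significantly positive mean does show that CPAS has not normalised, even if it has fallen a long way.

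The 44% figure should not be read as the study's power. It assumes SD 66 g and n=100, and 17.3 uses n=100 only as the number at which 90% power is reached. If more patients are recruited the figure rises, as the table shows.

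Finally, it is tempting to describe a fall in CPAS as albumin that has returned. Section 5.3 says that CPAS reflects capillary leakage or catabolism. Section 5.4 gives healthy synthesis as 13 g per 24 h, or 7 × 13 = 91 g over seven days, against a pilot shift of 48 g. How the calculation credits synthesis cannot be seen, because the figure in 11.1 is not shown. The change in CPAS can be estimated; calling it returned albumin is not supported.

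**Conclusion.** The point holds in two limited parts. The primary aim in 6.1 is worded so that the planned test could refute it but never confirm it, while the summary, 7.1 and 17.3 pose a question that the test does answer. The secondary aim of comparing POD 7 with EOS and POD 3 has no analysis that measures change.

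The size of the first part depends on unknowns. Under the assumed residual of 12 g, the chance of a significant result runs from 44% (SD 66 g, n=100) to above 99% (SD 33 g, n=150 or more). These figures show how far a null result depends on scatter and sample size; they do not predict the outcome. The second part needs no numerical assumption, because it follows from what a correlation is.

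The study describes itself as exploratory and hypothesis generating, and the sample-size calculation is correct. This is a minor-to-moderate point about matching aim, question and analysis.

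**What to change.** 1. Reword the primary aim in 6.1 to match 7.1, so that it asks whether mean CPAS is positive at POD 7.
2. In 17.2, name the primary analysis and its null value of zero, report mean POD 7 CPAS with its 95% CI, and state that a non-significant result will not be interpreted as normalisation. No equivalence margin is needed once the aim is reworded.
3. For the secondary aim, replace or supplement the correlation in question 1 of 7.2 and in 17.2 with the mean paired within-patient change in CPAS from EOS to POD 7 and from POD 3 to POD 7, each with a 95% CI.
4. Do not add a fraction-returned measure. A ratio is unstable when early CPAS is small (section 5.3 cites a range of 2 to 61 g after major abdominal surgery), and it is not clearly identifiable as returned albumin.

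The cost is a few sentences and two paired estimates. CPAS at EOS, POD 3 and POD 7 is already an endpoint in 8.1 and 8.2, so no extra patients, samples or visits are needed.

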6.2 PLANNED SUB STUDIES

Within this heterogeneous group of patients we plan to do subgroup analyses in some pre-defined groups. In addition we plan to study synthesis rate of albumin, the capillary leakage and lymphatic return as secondary outcomes.

Sub study A, Children < 18 years

The aim is to find if cumulative perioperative loss of albumin from plasma is positive at EOS, POD3 and POD7 respectively, after liver transplantation.

Sub study B, Adults in need of prolonged ICU stay

The aim is to investigate if cumulative perioperative loss of albumin from plasma is different at EOS, POD3 and POD7, respectively, in adults in need of prolonged ICU stay compared to adults not in need of prolonged ICU stay after liver transplantation.

7 RESEARCH QUESTION

7.1 PRIMARY QUESTION

Is cumulative perioperative loss of albumin from plasma positive at post-operative day 7 (4-10) after liver transplantation?

7.2 SECONDARY QUESTIONS

1. Does perioperative loss on POD7 (4-10) correlate to losses at EOS and POD3?
2. Is cumulative perioperative loss of albumin from plasma still positive at hospital discharge (or POD 21) following liver transplantation?
3. Dichotomize patients in two equally sized groups depending on the amount of cumulative loss of albumin from plasma on EOS, POD3 and POD7 respectively, i.e. to a "leaky" and a "less leaky" group. Which factors predict "leakiness" (demographics, bleeding, fluid balance, ascites, ELISAs etc)?

4. Is cumulative perioperative loss of albumin from plasma positive at EOS, POD3 and POD7 (4-10), respectively, after liver transplantation in children? This is the primary question in the children substudy .
5. Does perioperative loss on POD7 (4-10) correlate to losses at EOS and POD3 in children after liver transplantation?
6. Which factors characterize children with large postoperative drain losses after liver transplantation?
7. Does cumulative perioperative loss of albumin from plasma at EOS, POD3 and POD7 (4-10), respectively, differ between adults in need or not in need of prolonged ICU stay, respectively, after liver transplantation? This is the primary question in the prolonged ICU substudy.
8. Which factors predict “need of prolonged ICU stay” after liver transplantation (demographics, bleeding, fluid balance, ascites etc)?
9. How does synthesis rate of albumin develop during prolonged ICU stay?

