17.2 STATISTICAL ANALYSIS

In a previous study on selected patients undergoing liver transplantation at our department, we found a net leakage of albumin of 37 ± 17 g at end of surgery and of 48 ± 33 g at the third postoperative day. In our hospital, post-operative albumin infusions to keep plasma albumin at 25 g/l are very common, suggestive of ongoing losses in this patient group.

The effect and time course of ischemic liver injury on albumin synthesis has not been investigated, but in the previous pilot study albumin synthesis was higher than normal values on post-operative day 3. All data will be presented as mean with standard deviation (SD) or as median and range of data if not normally distributed.

Furthermore, the mutual correlations between the mass balance albumin parameters and albumin synthesis and P-albumin will be calculated and presented with correlation coefficients. Patients will be dichotomized to “leaky” and “not so leaky”, and possible predictors analyzed by univariate and multivariate logistic regression.

With 103 subjects there is a power of 80% to detect an anticipated effect size of 0.11 with 3 predictors and a 2-sided significance level of 5%. This equals the situation where the 3rd predictor gives an increase in the squared correlation coefficient r^2 from 0.30 to 0.37 or from 0.50 to 0.54. Although this is rather hypothetical it seems likely that such inferences might occur, and we will find them if 2 years production of liver transplants are investigated. If only 2 predictors are used an effect size of 0.095 can be found with 80% power.

Correlations will be reported as Pearson's correlation coefficient r or Spearman's rank correlation r_s depending on the data's nature.

Demographic preoperative data such as age, height, weight, BMI, gender, routine lab, history of weight loss, diagnoses, and current medications will be presented as numbers, averages and standard deviation, or as median range as applicable.

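### The secondary aim of comparing POD7 albumin loss with EOS and POD3 is analysed only by correlation, so the within-patient change has no planned paired estimate or confidence interval

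*Combined protocol and SAP*

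**What the plan says.** Section 6.1 states the aim as a comparison: "Secondary aims are to compare the loss at POD 7 with that at EOS and POD 3". In 7.2, question 1 turns it into an association: "Does perioperative loss on POD7 (4-10) correlate to losses at EOS and POD3". Question 5 asks the same in children.

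The analysis text in 17.2 follows 7.2:

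- "the mutual correlations between the mass balance albumin parameters and albumin synthesis and P-albumin will be calculated and presented with correlation coefficients". The coefficient is Pearson's r "or Spearman's rank correlation r_s depending on the data's nature".
- For description: "All data will be presented as mean with standard deviation (SD) or as median and range of data if not normally distributed".

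Section 8.2 lists the cumulative balance at EOS, POD3 and discharge as separate levels, with no change score. The only test of location named is in the power paragraph of 17.3, for the POD7 total against zero: "with a one sample 2-sided t-test and a significance level of 5" per cent. The regressions in 17.2 and 17.3 relate leakiness to predictors. Question 7 and sub study B compare ICU groups at each time point. None of these compares time points within patients.

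**The concern.** Comparing two cumulative totals asks how much the total changed. Correlating them asks whether patients who were high early are also high later. A plan can answer the second fully and leave the first open.

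This matters because the primary aim in 6.1 is whether "cumulative perioperative albumin shift is normalized on POD 7", while the planned test asks only whether the POD7 total differs from zero. A total above zero on POD7 is compatible with a loss that has been falling, steady or rising since POD3. The comparison in 6.1 is the part of the plan that would help to tell these apart. It is also the part without a matching analysis.

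**Working it through.** **1. The plan's own figure.** Section 17.3 states 90% power with n = 100, effect size 0.33, one-sample two-sided t-test at 5%. The noncentral t distribution gives 90.5%, and 99 subjects are enough for 90%. The figure is sound. It concerns the POD7 level against zero; the plan states no figure for a change between time points.

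**2. What a correlation can show.** Pearson's r is computed from deviations about each mean, and Spearman's coefficient from ranks. Adding a constant c to every POD7 value alters neither, while the mean change moves by c. As a check, 100 patients were simulated with an early total of mean 37 and SD 17 g and a later total of mean 48 and SD 33 g. Shifting all later values by -48 g or by +30 g left r at 0.424, while the mean change was -39.1 g or +38.9 g.

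**3. What the separate summaries can show.** If the same patients contribute at both times, the difference between the two means is the mean within-patient change. Its precision needs the SD of the change:

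SD(change) = √(SD₁² + SD₂² − 2·r·SD₁·SD₂)

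A reader could rebuild this only from both SDs and Pearson's r on the same patients. It cannot be rebuilt from Spearman's coefficient or from medians with ranges, both of which 17.2 allows.

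**4. Size, from the only pair of time points with figures.** Section 17.2 gives "a net leakage of albumin of 37 ± 17 g at end of surgery and of 48 ± 33 g" at the third postoperative day. Mean rise = 48 − 37 = 11 g. The within-patient correlation is not given, so its whole range is shown. The number of complete pairs is assumed to be 100, the n used in 17.3. Half-width = 1.984 × SD(change)/√100.

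| Assumed r | SD of change (g) | 95% CI half-width (g) | CI around 11 g |
|---|---|---|---|
| 1 | 33 − 17 = 16.0 | 3.2 | 7.8 to 14.2 |
| 0.9 | 19.2 | 3.8 | 7.2 to 14.8 |
| 0.5 | √(289 + 1089 − 561) = 28.6 | 5.7 | 5.3 to 16.7 |
| 0 | √(289 + 1089) = 37.1 | 7.4 | 3.6 to 18.4 |
| −1 | 33 + 17 = 50.0 | 9.9 | 1.1 to 20.9 |

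The same two means and SDs thus fit intervals that differ about threefold in width. Treating the two summaries as independent amounts to taking the r = 0 row.

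**5. POD7.** The documents give neither a mean nor an SD at POD7, so no corresponding figure can be derived for the two comparisons that 6.1 names.

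**The case against.** **Intent.** The aim in 6.1 is one line, 7.2 is the operational list, and correlation is asked for twice there and planned in 17.2. The word compare may be loose. This stands as a possibility, and the fix allows for it. The literal reading is still the better one: section 5.2 reports that in the pilot the loss appeared to continue beyond surgery, so the time course is part of the motivation. On either reading 6.1 and 7.2 need to be reconciled.

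**The means will be reported anyway.** This stands in part. A reader might infer that the plan yields no estimate of the change at all. That is too strong, because subtracting the planned means gives a crude one. What is missing is a planned paired estimate with its precision.

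**The study is exploratory and the statistics section is brief throughout.** This is true and limits the weight of the point. It does not remove it: for this aim a method is named, and that method answers a different question.

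**The primary test.** A reader might infer that the one-sample test would almost certainly read positive whether POD7 loss had fallen to 20 g, stayed at 48 g or risen to 76 g. The documents do not support this without a limit on the POD7 SD, which they do not give. At n = 100 and a mean of 20 g, power is 91% for an SD of 59.9 g, but 86% for 65.4 g and 76% for 74.6 g.

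**Limits of the remedy.** With POD7 defined as days 4 to 10, the interval after POD3 runs from 1 to 7 days, so a paired change does not cleanly measure a rate. This stands, and is why the actual day should be reported.

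**Conclusion.** The point holds for one secondary aim. Section 6.1 promises a comparison between time points. Sections 7.2 and 17.2 supply only a correlation, which cannot show the direction or size of the change, and no paired estimate or confidence interval is planned anywhere.

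The size is illustrative. It rests on the pilot SDs, on 100 complete pairs and on an unknown correlation, and it concerns EOS to POD3 rather than the POD7 comparisons themselves. The gap in the plan does not depend on those figures.

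A reader might go further and infer that the primary conclusion or the sample size is undermined. The documents do not support that: the primary question concerns the POD7 total against zero, and its power statement reproduces. This is a change worth making, not a fatal defect.

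**What to change.** In 17.2, name the within-patient differences POD7-POD3 and POD7-EOS in the main cohort as the analysis of the 6.1 aim. For each, report:

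- the number of pairs;
- the mean difference with a 95% CI or, if the differences are not normally distributed, the median difference with its CI and a signed-rank test;
- the actual postoperative day used, taking the same POD7 (4-10) value as the primary endpoint.

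Keep the correlations of questions 1 and 5 as description. Note beside them that the later total contains the earlier one, so a positive r does not by itself show that early loss predicts further loss.

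If the authors meant only correlation, reword 6.1 to match 7.2 and claim no comparison.

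The cost is wording and a little more analysis. The EOS, POD3 and POD7 totals are already endpoints, so no new data are needed. The downsides are that pairs are limited to patients with both values, and that the POD7-POD3 change mixes rate with an interval of 1 to 7 days.
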